
Study Objectives:
 
 • Primary: • Secondary: 	
The primary objective is to ascertain if addition of Saxagliptin improves endothelial dysfunction in early type 2 diabetes patients.
 
The secondary objective is to establish CD34+ cell number, function and gene expression as important bio-markers to monitor endothelial function.

Study Design:
	
Prospective, double-masked, randomized placebo-controlled trial

Accrual Goal: (Total number of subjects)	N=42
Accrual Rate: (Number of subjects expected per month)	Recruit 42 patients in approximately 36 months.
Estimated: FPFV: LPFV: Follow Up: (dd-mm-yy)	FPFV: 01-10-12. LPFV: 01-06-15
Correlative Studies: (PK/PD, etc.)	N/A
Inclusion Criteria:	
 1. Adults aged 40-70 years. 2. Diagnosis of type 2 diabetes within the previous 8 years using criteria of the American Diabetes Association 3. Currently treated with no hypoglycemic agents other than a stable dose (>3 months) of metformin (≥ 1.0 to ≤ 2 grams daily). 4. HbA1C between 6 to 9% (both inclusive) 5. BMI 25 to 39.9 kg/m² (both inclusive)

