²⁰where Sitagliptin was compared to placebo with endothelial progenitor cells as a outcome measure in patients with type 2 diabetes over 4 weeks. Though our study is over 12 weeks we do not anticipate significant drop in HbA1C in between the two groups in this relatively short time period to act as a confounding factor on CD34+ cell number, function and gene expression. Most clinical studies looking at HbA1C reduction were of a much longer duration of 6 months or above and most DPP-4 inhibitor studies are with animal EPCs where comparison with human CD34+ population is difficult to make. In one study⁵⁸ where saxagliptin was used for 12 weeks in drug-naïve type 2 diabetes patients there was placebo-subtracted HbA1c reduction noted of 0.45-0.63%. It showed mean placebo-subtracted reductions in fasting serum glucose of 20 mg/dL. From our laboratory studies of in vitro human EPC studies we do not think glucose level change of 20 mg/dL is significant enough to account for changes in EPC number, function and gene expression. However we will take this possibility into account during statistical analysis of the results between the saxagliptin and placebo groups.

Lifestyle Intervention for Type 2 diabetes patients²:

To keep uniformity within the cohort regarding lifestyle during the length of the study duration, all patients at entry will ideally receive dietary advice from the research coordinator, a diabetes educator, a registered dietitian (as per American Diabetes Association clinical guidelines²), specifically geared towards type 2 diabetes patients. They will be advised to adhere to 150 minutes of weekly aerobic exercise (50-70% of maximal heart rate) as best as possible. Patient's activity will be monitored using accelerometers and will be downloaded at regular intervals by the research coordinator.

Subjects will be taking 5.0 mg of Onglyza (saxagliptin) or placebo. We choose to use the maximum approved dose of saxagliptin in order to discern a definite effect.

Visits with outcome measurements will be scheduled for morning following overnight 10 hours fast to reduce diurnal variability, and clinical parameters will be obtained at scheduled office visits as depicted in the study schema and will be measured at each outcome visit as follows:

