The distributional assumptions of all measures will be examined. Means and standard deviations will be computed for continuous measures and proportions for categorical variables. Graphical representations of the mean group slopes and individual slopes will be generated and inspected. Study groups will be compared to determine whether any imbalance between the groups on patient characteristics remain after randomization. If imbalance is evident, by inspection, all models will be adjusted for the unbalanced covariates. Change in outcome over time will be examined using a multilevel approach with linear mixed models (LMM)^{53,54}. The longitudinal multilevel modeling approach will enable us to examine characteristics of within-person change, as well as between-group differences that may influence change. LMMs handle missing data more efficiently than traditional ANOVA designs. In the linear mixed models, the patient is considered a random effect and the outcome measured at specific time points is nested within patient. In an initial model containing only the variable TIME, we will use a likelihood ratio test to determine whether a random effect for time should be modeled. The model below represents a random intercept for patient and a random coefficient for TIME.

$$Y_{ij} = \beta_0 + \beta_1 Time_{ij} + u_{i0} + u_{i1} Time_{ij} + \varepsilon_{ij}$$

We will examine whether TIME may be modeled linearly by testing the added contribution of TIME (represented with two indicator variables) to a model with TIME as a single continuous variable. Assuming time may be modeled as a continuous variable, subsequent analyses will add study group and other patient characteristics as covariates. We are particularly interested in whether there is a significant interaction between study group and time, adjusting for other patient level covariates. A significant interaction would indicate that the slopes in outcome over time differ by study group. If the global test of interaction is significant, subsequent significance testing of the pair wise comparisons of group slopes group will be adjusted for multiple comparisons. The model also includes coefficients for the group-by-time interactions and random effects for patient and time.

$$Y_{ij} = \beta_0 + \beta_1 Time_{ij} + \beta_2 Group_i + \beta_3 (Time_{ij} \times Group_i) + u_{i0} + u_{i1} Time_{ij} + \varepsilon_{ij}$$

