In the event that TIME is modeled using indicator variables, two indicator variables will be used to represent the three time points, with baseline serving as the reference category. The interaction between GROUP and TIME will be modeled in a similar fashion using two additional indicator variables. The above multivariable model enables us to adjust for time-varying covariates, such as glucose. Since glucose will be measured contemporaneously with the outcomes at each visit, however, causal interpretations of glucose and any outcome are suspect. As such, we will consider glucose as a nuisance covariate, and consider any relationship between glucose and an outcome as merely associative.

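### Section 8 leaves the group-by-time comparison open to adjustment for on-treatment glucose and does not say whether the adjusted or the unadjusted interaction answers the primary objective

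*Combined protocol and SAP*

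**What the plan says.** The synopsis sets the question without any condition on glucose: "The primary objective is to ascertain if addition of Saxagliptin improves endothelial dysfunction in early type 2 diabetes patients". Section 1.3 and the expected results in Section 4.1 pose a second question, whether there is an effect on endothelial progenitor cells (EPCs) beyond glycaemic control.

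Under Data Analysis, Section 8 makes the group-by-time interaction the comparison of interest, adjusted for patient-level covariates that it does not list. The displayed equation contains time, group, their product, a random intercept and a random slope, but no glucose. A likelihood ratio test decides whether the random slope stays. If linearity in time fails, "In the event that TIME is modeled using indicator variables, two indicator variables will be used to represent the three time points"; that version is also described without glucose. Section 8 then adds "The above multivariable model enables us to adjust for time-varying covariates, such as glucose", notes that glucose is measured at the same visits as the outcomes, and concludes "we will consider glucose as a nuisance covariate, and consider any relationship between glucose and an outcome as merely associative".

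The Study Design Overview in Section 6.2 cites a 12-week saxagliptin study in drug-naive patients: "It showed mean placebo-subtracted reductions in fasting serum glucose of 20 mg/dL". The authors state that "we do not think glucose level change of 20 mg/dL is significant enough to account for changes in EPC number", and continue: "However we will take this possibility into account during statistical analysis of the results between the saxagliptin and placebo groups".

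**The concern.** There are two questions and two candidate models, and the plan does not match them up. Randomisation supports the unadjusted interaction as an estimate of the effect of adding saxagliptin. The glucose-adjusted interaction conditions on a variable measured after randomisation that the drug is expected to change, and so it may estimate something else.

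The caveat in Section 8 concerns the association between glucose and an outcome. It does not address what conditioning on glucose does to the group-by-time coefficient, which is the quantity the trial is run to estimate.

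With neither fit labelled primary, either could be presented as the main result once the data are known. Separately, a glucose-adjusted coefficient could be read as an effect beyond glycaemic control without the assumption that reading needs, namely that glucose and the cells share no unmodelled causes.

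**Working it through.** **1. The plan's own figure.** Inputs from Section 8: SD 15, correlation 0.60, visits at weeks 0, 6 and 12 (sum of squared time deviations 72), 18 per group, slopes of 4 and 5 cells per week.

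- SE of the slope difference = √[2 × 15² × (1 − 0.60) / (18 × 72)] = √(180/1296) = 0.373.
- 1/0.373 = 2.683. Power is Φ(2.683 − 1.645) = 0.85 one-sided and Φ(2.683 − 1.960) = 0.77 two-sided, against the stated 84%.

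The stated figure matches a one-sided 5% test. Sidedness is not stated, which is a separate matter. What counts here is that the calculation has no glucose term: the trial was sized for the unadjusted slope difference of 1 cell per week, or 12 cells at week 12.

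**2. When the two interactions agree.** Let D be the placebo-subtracted glucose fall at week 12 and b the fitted glucose coefficient (cells per mg/dL). With linear changes,

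adjusted week-12 difference = unadjusted difference + b × D.

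The expected shift is zero if D = 0. It is also zero if b = 0, which holds when glucose neither affects the cells nor shares unmodelled causes with them. Otherwise the two generally differ.

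**3. If glucose affects the cells.** Suppose a share f of the 12 cells acts through glucose and there are no shared causes. The adjusted interaction then targets 12 × (1 − f): 9 cells at f = 0.25 and 6 cells at f = 0.50. The documents do not give f.

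**4. If glucose and the cells only share causes.** Diet and exercise are possible examples, since both are part of the lifestyle intervention.

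- From the plan: within-patient variance 225 × 0.40 = 90 (SD 9.49); between-patient variance 225 × 0.60 = 135 (SD 11.62).
- Assumed, not in the documents: no effect of glucose on the cells; D = 20 as in the cited study; within-patient glucose SD 20; between-patient glucose SD 30; within-patient correlation r between −0.4 and +0.4; random intercept only.

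In large samples with three visits per patient,

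b = [2Cw/φw + (Cw + 3Cb)/φb] / [2 × 400/φw + (400 + 3 × 900)/φb],

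where Cw and Cb are the within- and between-patient covariances, φw = 90 − 2bCw + 400b², and φb = 495 − 2b(Cw + 3Cb) + 3100b². For r = +0.4, Cw = 0.4 × 9.49 × 20 = 75.9.

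- Between-patient correlation also 0.4: Cb = 0.4 × 11.62 × 30 = 139.4, φw = 75.7, φb = 417.2. Then b = (2.005 + 1.185)/(10.57 + 7.43) = 0.177, a shift of 0.177 × 20 = 3.5 cells.
- Between-patient correlation zero: Cb = 0, φw = 77.0, φb = 527.7. Then b = (1.971 + 0.144)/(10.39 + 5.87) = 0.130, a shift of 2.6 cells.

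For r = −0.4 the signs reverse. Simulation of the random-intercept model (5,000 trials per case) gave week-12 differences of 8.45 and 15.55 with equal correlations, 9.39 and 14.60 with zero between-patient correlation, and 11.97 at r = 0. Coding time with indicators gave the same values to within 0.02.

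**5. What makes it smaller.** With D = 10 the shifts halve to about 1.8 and 1.3 cells. If a random slope is kept, with an assumed slope variance of 0.5 and the total slope variance held fixed, they fall to roughly 3 and 2 cells.

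**The case against.** The strongest reply is that the plan is already unadjusted. The only group-by-time equation has no glucose term, and the wording on glucose states what the model can do. That stands: a reader might infer that the plan commits to a glucose-adjusted primary analysis, and the documents do not support that. But Section 6.2 says a glucose difference will be allowed for in the between-arm comparison, and the unadjusted fit is nowhere named as primary.

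Second, the authors expect no important between-arm HbA1c difference and regard 20 mg/dL as too small to explain a change in the cells. If they are right on either count, and there are no shared causes, the two estimates agree. However, the same part of Section 6.2 reports a placebo-subtracted HbA1c reduction of 0.45 to 0.63% at 12 weeks in the cited study, and Section 1.1.5 describes clinically meaningful falls in fasting glucose at 5 mg. Some lowering is therefore the expected case, although the cited study was in drug-naive patients and this trial adds saxagliptin to metformin. The authors' view on 20 mg/dL also does not cover shared causes.

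Third, the hypothesis in Section 1.3 is an effect beyond glycaemic control, so the adjusted model has a proper purpose. That stands as well, and is why the model should be kept and labelled. The synopsis objective carries no such condition, and the sample size was computed without glucose.

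A reader might also infer that adjustment must hide a real effect. The documents do not show that. The shift can go either way or be zero, and its size depends on inputs they do not give.

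**Conclusion.** The concern holds as a gap in specification that should be fixed. The plan signals possible adjustment of the randomised comparison for on-treatment glucose and does not say which interaction answers which question. The adjusted interaction equals the total effect of adding saxagliptin if the drug does not shift glucose differently between arms, or if glucose neither affects the cells nor shares unmodelled causes with them. Otherwise it generally differs, and with shared causes it is not a valid direct effect either.

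The shift of 2.6 to 3.5 cells on a planned 12 is an illustration, not a prediction. It rests on the assumed glucose SDs, correlations and 20 mg/dL fall, and on the random-intercept branch only. The plan's model may keep a random slope, and the fall on top of metformin may be smaller; either would reduce the shift.

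**What to change.** In Section 8, state that the primary analysis for the synopsis objective is the group-by-time interaction from the displayed model, or from its indicator-time version if linearity is rejected, with no post-randomisation covariate. State that any covariates in that model are baseline values listed before unblinding. The sentence "If imbalance is evident, by inspection, all models will be adjusted for the unbalanced covariates" should be made consistent with that list for the primary model.

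Keep the time-varying-glucose model as a labelled supportive analysis of the hypothesis of an effect beyond glycaemic control. State its assumption that glucose and the cells share no unmodelled causes, and do not rest that conclusion on this model alone.

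The cost is a few sentences and no new data. The one real concession is that the glucose-adjusted result becomes supportive and can no longer be offered as the main answer.

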9 STUDY MANAGEMENT

9.1 Compliance with the Protocol

9.1.1 Compliance with the Protocol and Protocol Revisions

The study shall be conducted as described in this approved protocol. All revisions to the protocol must be discussed with, and be prepared by, BMS. The investigator should not implement any deviation or change to the protocol without prior review and documented approval/favorable opinion from the IRB/IEC of an amendment, except where necessary to eliminate an immediate hazard(s) to study subjects.

If a deviation or change to a protocol is implemented to eliminate an immediate hazard(s) prior to obtaining IRB/IEC approval/favorable opinion, as soon as possible the deviation or change will be submitted to:

- IRB/IEC for review and approval/favorable opinion
- AstraZeneca Pharmaceuticals LP
- Regulatory Authority(ies), if required by local regulations

Documentation of approval signed by the chairperson or designee of the IRB(s)/IEC(s) will be sent to BMS.

If an amendment substantially alters the study design or increases the potential risk to the subject: (1) the consent form will be revised and submitted to the IRB(s)/IEC(s) for review and approval/favorable opinion; (2) the revised form will be used to obtain consent from subjects currently enrolled in the study if they are affected by the amendment; and (3) the new form must be used to obtain consent from new subjects prior to enrollment.

If the revision is an administrative letter, investigators must inform their IRB(s)/IEC(s).

9.2 Records Retention

9.2.1 Records Retention

The investigator will retain all study records and source documents for the maximum period required by applicable regulations and guidelines, or institution procedures, or for the period specified by BMS, whichever is longer.

If the investigator withdraws from the study (e.g., relocation, retirement), the records shall be transferred to a mutually agreed upon designee (e.g., another investigator, IRB). Notice of such transfer will be given in writing to BMS.

9.2.2 Study Drug Records

Investigator will ensure that a current disposition record of investigational product (those supplied by the BMS) is maintained at each study site where study drug and non investigational product(s) is/are inventoried and dispensed. Records or logs will comply with applicable regulations and guidelines and will include:

- amount received and placed in storage area
- amount currently in storage area
- label ID number or batch number
- amount dispensed to and returned by each subject, including unique subject identifiers
- amount transferred to another area/site for dispensing or storage
- non-study disposition (e.g., lost, wasted)
- amount destroyed at study site, if applicable
- amount returned to the AstraZeneca Pharmaceuticals LP
- retain samples for bioavailability/bioequivalence, if applicable

- dates and initials of person responsible for Investigational Product (IP) dispensing/accountability, as per the Delegation of Authority Form.

10 GLOSSARY OF TERMS

Term	Definition
Adverse Reaction	An adverse event that is considered by either the investigator or the sponsor to be related to the investigational product
Expedited Safety Report	Rapid notification to investigators of all SAEs that are suspected (related to the investigational product) and unexpected (i.e., not previously described in the Investigator Brochure), or that could be associated with the study procedures.
SUSAR	Suspected, Unexpected, Serious Adverse Reaction as termed by the European Clinical Trial Directive (2001/20/EC).
Unexpected Adverse Reaction	An adverse reaction, the nature or severity of which is not consistent with the applicable product information (e.g., Investigator Brochure for an unapproved investigational product)

11 LIST OF ABBREVIATIONS

A1C	Glycosylated Hemoglobin
AE	Adverse Event
BMS	Bristol-Myers Squibb
CYP3A4	Cytochrome P450 3A4
DPP-4	Dipeptidyl peptidase 4
ESR	Expedited Safety Report
FDA	Food and Drug Administration
FSH	Follicle-Stimulating Hormone
GCP	Good Clinical Practice
GIP	Glucose dependent insulinotropic peptide
HCG	Human Chorionic Gonadotropin
HRT	Hormone Replacement Therapy
IB	Investigator Brochure
ICH	International Conference on Harmonisation
IEC	Independent Ethics Committee
IND	Investigational New Drug (Application)
IRB	Institutional Review Board
IST	Investigator-Sponsored Trial
MWG	Mean Weighted Glucose
NSAE	Non-Serious Adverse Event
PPG	Post-Prandial Glucose
SAE	Serious Adverse Event
SU	Sulfonylurea
SUSAR	Suspected Unexpected Serious Adverse Reaction
TDZ	Thiazolidinedione
WOCBP	Women of Child-Bearing Potential

